All sessions are in-person and videorecorded. Participants must pass a listening check to proceed with the session. Sessions take place in a quiet room (ambient noise ≤ 40 dB as measured by a sound level mobile application) in the child's home, educational setting, or clinic, depending on caregiver preference. Flexibility in location to match caregiver preferences is one way we guard against attrition. Having the examiner for all assessments and intervention sessions be a research team member, rather than school personnel, and conducting the intervention for a relatively short period of time are also designed to guard against attrition.

Dependent Variable Probe

The dependent variable probes (about 10 minutes) test the 12 target words in sets by condition. The primary dependent variable is the percent accuracy (i.e., correct responses / total trials x 100) for labeling target words expressively. The examiner asks the child to label the taught unfamiliar objects and one known object per set (i.e., "What's this?"). The participant is given up to 10 seconds to respond. The secondary dependent variables are the percent accuracy for (a) receptively identifying target words within 5 seconds in a field of six (i.e., four target objects, one foil, and a known object), (b) associated semantic information (i.e., location; "Where's this from?"), and (c) phonological precision for labeling target words expressively. The examiner will not provide any feedback regarding response accuracy for target words during the dependent variable probes. To maintain engagement, the examiner may provide positive reinforcement for non-target behaviors and for identifying the known word for each group, which is expected to be particularly important in the early sessions when accuracy for target words is expected to be low. The study's procedural manual specifies how the examiner should respond to specific child behaviors (e.g., self-corrections and articulatory errors). Primary and secondary coders double enter data into an electronic form using direct systematic observation of the video recordings (Ledford & Gast, 2018).

A research assistant codes at least 25% of sessions in each condition for each participant for interobserver agreement (IOA). The primary coder is blind to which sessions are coded for reliability. All coders are trained to .85 point-by-point agreement for independent coding of three consecutive sessions via recordings of non-participants

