(Ledford & Gast, 2018). Training includes reading the coding manual, a didactic presentation, and group coding of non-participants with discrepancy discussions prior to independent coding. Discrepancy discussions occur regularly. If IOA falls below .85 for two sessions, coders must re-train to the initial training criteria.

Baseline Phase

Baseline sessions will occur three times per week and continue until the participant demonstrates a stable pattern of response, with a minimum of three sessions (Ledford & Gast, 2018). Participants complete a listening check then the dependent variable probe to test learning of the 12 target words.

Comparison Phase

Comparison phase sessions occur three times per week after the baseline phase is complete. They begin with a listening check, then the dependent variable probe, and then the two retrieval practice intervention conditions (i.e., feedback-massed, no feedback-massed, feedback-spaced, and no feedback-spaced) for the participant's specific, randomly assigned contrast. In each session, the second condition occurs immediately after the first. Participants are taught the meaning of novel nouns (Lund & Douglas, 2016; Reimer, 2019; Storkel et al., 2019). The independent variable that differentiates the conditions is either the presence of feedback or spaced versus massed trials. All other potentially influential variables are held constant. Table 1 provides a summary of the key teaching procedures for the massed trials conditions (with and without feedback). For the massed trials conditions, all exposures for one word are provided before presenting the next word in an order determined via a random number generator. The spaced trials conditions proceed in the same manner with the exception that the exposures for the four target words are interspersed with one another (e.g., an exposure for word 1, then one for word 3, then one for word 2, etc.). The interspersing of trials across words is especially apparent through the color coding of the steps by word in the Teaching Sessions section of the procedural manual.

Table 1

Summary of Teaching Procedures for Massed Trials Conditions

1. Examiner shows novel object, labels it, and states its location (e.g., "This is a X. The X is from the park.")
2. Examiner and participant color pictures of each novel object to provide shared context
3. Examiner says the label for the novel object ten more times and its location three more times

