4. Examiner asks the participant to label the novel object four times and the location twice for retrieval practice

Feedback condition: Examiner provides direct feedback on accuracy and labels the target word (e.g., "Yes, that is a X!" or "Oops, that is a X!")

No-feedback condition: Examiner says statement without target word and then one with it to provide equal exposures to the feedback conditions (e.g., This looks neat. Here's the X!)

5. After the first word, examiner completes same procedure with the three remaining target words in the set
6. Examiner concludes set by asking participant to label and identify the picture for each word and state its location

Feedback condition: Examiner provides direct feedback without naming the target word

No-feedback condition: Examiner does not provide feedback and proceeds to next item

After a participant reaches the criterion of 75% accuracy for expressive labeling for three consecutive sessions for the four target words for one condition, instruction in the remainder of the comparison phase is provided only in the unmastered condition. The comparison phase ends when the unmastered condition reaches criterion. If the participant does not reach mastery after two times the number of sessions to criterion in the mastered condition, the maintenance phase begins then.

Maintenance Phase

Maintenance data are collected weekly via baseline procedures. Maintenance data are first collected a week after the participant achieves mastery for at least one condition. The same dependent variable probe used for the baseline and comparison phases is used to collect maintenance data. Sessions continue for 4 weeks after the comparison phase to permit sufficient time for a trend to emerge for visual analysis. If a consistent pattern is observed before 4 weeks have elapsed, the maintenance phase will end at that time. For example, the maintenance phase ends if a participant exhibits 0% accuracy for all conditions for two consecutive sessions.

Procedural Fidelity

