Contrasts to Determine Effect of Spacing (RQs 7-12)	Contrast D: Spaced vs. massed trials (with feedback)	Contrast C: Spaced vs. massed trials (no feedback)	

Table 2. *Comparisons of Relevant Conditions for the Effect of Feedback*

Research question		Contrast	Condition 1	Condition 2	Phase	Feedback RQs
Effectiveness or efficiency	Acquisition or retention					
Effectiveness	Acquisition	A	Feedback w/massed trials	No-teaching control	Comparison	1
		B	Feedback w/spaced trials	No-teaching control	Comparison	1
		A	No feedback w/massed trials	No-teaching control	Comparison	2
		B	No feedback w/spaced trials	No-teaching control	Comparison	2
Effectiveness	Retention	A	Feedback w/massed trials	No-teaching control	Maintenance	3
		B	Feedback w/spaced trials	No-teaching control	Maintenance	3
		A	No feedback w/massed trials	No-teaching control	Maintenance	4
		B	No feedback w/spaced trials	No-teaching control	Maintenance	4
Efficiency	Acquisition	A	Feedback w/massed trials	No feedback w/massed trials	Comparison	5
		B	Feedback w/spaced trials	No feedback w/spaced trials	Comparison	5
Efficiency	Retention	A	Feedback w/massed trials	No feedback w/massed trials	Maintenance	6
		B	Feedback w/spaced trials	No feedback w/spaced trials	Maintenance	6

Effectiveness. For research questions related to effectiveness, we determine whether there is an increase in accuracy for the active retrieval practice condition without an

accompanying increase, or with a smaller increase, for the no-teaching control condition. Given that the target words are novel words, participants are not expected to show increased accuracy for the dependent variables for the control condition.

For effectiveness of retrieval practice with feedback for *acquisition* (RQ1), we determine whether there is a separation of the data paths (as indicated by visual analysis and statistical analyses) for (a) the retrieval practice with feedback with massed trials condition and the no-teaching control condition and (b) the retrieval practice with feedback with spaced trials condition and the no-teaching control condition in the comparison phase. This separation of the data paths with the retrieval practice condition above the no-teaching condition in the comparison phase would provide evidence of the effectiveness of retrieval practice with feedback.

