For effectiveness of retrieval practice without feedback for *acquisition* (RQ2), we determine whether there is a separation of the data paths for (a) the retrieval practice without feedback with massed trials condition and the no-teaching control condition and (b) the retrieval practice without feedback with spaced trials condition and the no-teaching control condition in the comparison phase. This separation of the data paths with the retrieval practice condition above the no-teaching condition in the comparison phase would provide evidence of the effectiveness of retrieval practice without feedback.

For effectiveness of retrieval practice with feedback for *retention* (RQ3), we determine whether there is a separation of the data paths for (a) the retrieval practice with feedback with massed trials condition and the no-teaching control condition and (b) the retrieval practice with feedback with spaced trials condition and the no-teaching control condition in the maintenance phase. This separation of the data paths with the retrieval practice condition above the no-teaching condition in the maintenance phase would provide evidence of the effectiveness of retrieval practice with feedback for retention.

For effectiveness of retrieval practice without feedback for *retention* (RQ4), we determine whether there is a separation of the data paths for (a) the retrieval practice without feedback with massed trials condition and the no-teaching control condition and (b) the retrieval practice without feedback with spaced trials condition and the no-teaching control condition in the maintenance phase. This separation of the data paths with the retrieval practice condition above the no-teaching condition in the maintenance phase would provide evidence of the effectiveness of retrieval practice without feedback for retention.

Efficiency. For research questions related to efficiency, we determine whether there is faster attainment of the mastery criterion for one retrieval practice condition versus another and whether mastery-level performance is better maintained.

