For efficiency of retrieval practice with versus without feedback for *acquisition* (RQ5), we determine whether there is a separation of the data paths for (a) the retrieval practice with feedback with massed trials condition and the retrieval practice without feedback with massed trials condition (Contrast A) and (b) the retrieval practice with feedback with spaced trials condition and the retrieval practice without feedback with spaced trials condition (Contrast B) in the comparison phase. The number of sessions to mastery is

also considered when determining the presence of a functional relation related to efficiency. This separation of the data paths in the comparison phase would provide evidence of greater efficiency for the condition with the path that is displayed higher on the graph.

For efficiency of retrieval practice with versus without feedback for *retention* (RQ6), we determine whether there is a separation of the data paths for (a) the retrieval practice with feedback with massed trials condition and the retrieval practice without feedback with massed trials condition (Contrast A) and (b) the retrieval practice with feedback with spaced trials condition and the retrieval practice without feedback with spaced trials condition (Contrast B) in the maintenance phase. The number of sessions to fall below mastery is also considered when determining the presence of a functional relation related to efficiency. This separation of the data paths in the maintenance phase would provide evidence of greater efficiency for the condition with the path that is displayed higher on the graph.

Spacing. Participants ($n = 8$) in Contrasts C (spaced vs. massed trials without feedback) and D (spaced vs. massed trials with feedback) address the effect of spacing. Table 3 displays how we will compare conditions within Contrasts C and D to evaluate both effectiveness and efficiency research questions. As with the analyses for feedback, we use expressive labeling as the primary dependent variable. Phonological precision, receptive performance, and knowledge of semantic content are secondary variables that will be considered when interpreting the overall results.

Table 3. *Comparisons of Relevant Conditions for the Effect of Spacing*

Research question		Contrast	Condition 1	Condition 2	Phase	Spacing RQs
Effectiveness or efficiency	Acquisition or retention					
Effectiveness	Acquisition	C	No feedback w/spaced trials	No-teaching control	Comparison	7

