For efficiency of retrieval practice with spaced versus massed trials for *retention* (RQ12), we determine whether there is a separation of the data paths for (a) the retrieval practice without feedback with massed trials condition and the retrieval practice without feedback with spaced trials condition (Contrast C) and (b) the retrieval practice with feedback with massed trials condition and the retrieval practice with feedback with spaced trials condition (Contrast D) in the maintenance phase. The number of sessions to fall below mastery is also considered when determining the presence of a functional relation related to efficiency. This separation of the data paths in the maintenance would provide evidence of greater efficiency for the condition with the path that is displayed higher on the graph.

Statistical Analysis

There is no consensus on recommended statistical analyses for single case research designs, particularly for the adapted alternating treatments design, which is underrepresented in research on the use of statistical analyses and effect sizes in single case research. We will calculate Nonoverlap of All Pairs (NAP; Parker & Vannest, 2009), an overlap-based effect size, and analyze differences in conditions analogous to those described for visual analysis. Because overlap is one feature used for determining a functional relation, NAP will provide guidance on the degree of confidence for inferring the amount of overlap between conditions. NAP is defined as the number of comparison pairs between phases A and B without overlap divided by the total comparisons. It is related to Tau, another overlap metric. Tau is a linear re-scaling of NAP (Zimmerman et al., 2018). NAP offers several advantages over other overlap-based effect sizes, including less human error in calculations (can be calculated by hand or via computerized methods), stronger validation by R^2 , and narrower confidence intervals (Parker & Vannest, 2009). Parker and Vannest (2009) tentatively suggest the following guidelines for NAP effect sizes: .93 – 1.00 = large, .66 – .92 = medium, and 0 – .65 = weak.

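### Acquisition NAP counts a comparison-phase probe taken before any teaching, which pulls it toward .50 and can lower its size label; the tie and orientation rules should be written in the same edit

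*Combined protocol and SAP*

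**What the plan says.** Section 5.0 (Comparison Phase) fixes the order within each session: "They begin with a listening check, then the dependent variable probe, and then the two retrieval practice intervention conditions". A baseline session in the same section consists of the listening check and the same probe. Section 5.0 (Dependent Variable Probe) refers to reinforcement being important "in the early sessions when accuracy for target words is expected to be low".

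Section 8.0 judges acquisition on the comparison phase as a whole. For the effectiveness questions, the evidence is separation of the paths "with the retrieval practice condition above the no-teaching condition in the comparison phase". For RQ1 the plan speaks of "separation of the data paths (as indicated by visual analysis and statistical analyses", so the statistic has a stated part in the reading. For the control words, "participants are not expected to show increased accuracy for the dependent variables for the control condition".

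Under Statistical Analysis, NAP is to be computed for condition differences analogous to those in the visual analysis, with this definition: "NAP is defined as the number of comparison pairs between phases A and B without overlap divided by the total comparisons". The suggested bands are .93 to 1.00 large, .66 to .92 medium and 0 to .65 weak, and they are described as tentative. Ties are not mentioned. For RQs 5, 6, 11 and 12, separation "would provide evidence of greater efficiency for the condition with the path that is displayed higher on the graph". No sentence says which condition is A and which is B.

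**The concern.** The first comparison-phase probe comes before any teaching and follows the same steps as a baseline session. With novel words it should sit near 0% in every condition, so it says nothing about teaching. No sentence in Section 8.0 excludes it or assigns it to baseline, so an analyst who follows the plan includes it. It then produces ties and, between two active sets, losses for the better set. The result is pulled toward .50 for a reason unrelated to how well the child learned.

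What is at stake is the reported effect size and its label. A child who learns every word set cleanly can be reported with a medium effect because of one observation that belongs to baseline. Two related gaps act on the same number. The literal definition gives ties no credit, and the orientation for the four efficiency questions is not written for NAP. Two analysts could therefore report different values for the same child.

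**Working it through.** The plan reports no NAP value, so there is no figure to reproduce.

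**Inputs from the documents:** probe before teaching; mastery at 75% on three consecutive sessions; the comparison phase ends when the second set masters, or at the cap ("If the participant does not reach mastery after two times the number of sessions to criterion in the mastered condition"); the NAP bands.

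**Assumptions:** 0% on the untaught probe; control at 0% throughout; one labelling trial per word, so scores move in 25-point steps; bands applied after rounding to two decimals.

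**Shortest series.** With probe 1 at 0%, the earliest three consecutive probes at criterion are probes 2 to 4, so the phase can end at n = 4 if both sets master then.

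**1. Active versus control, every later active probe above 0%.** Each of the n − 1 later active probes beats all n control probes. The untaught probe ties with all n.
- Half credit: (n − 0.5)/n = 3.5/4 = .875; 5.5/6 = .917; 6.5/7 = .929 (rounds to .93, large); 7.5/8 = .9375.
- No credit: (n − 1)/n = 3/4 = .750; 7/8 = .875; 12/13 = .923; 13/14 = .929 (rounds to .93).
- Probe 1 removed: 1.00 at every n under either rule.

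The label is medium instead of large at 4–6 probes with half credit, and at 4–13 with none. At 8 probes the tie rule alone moves the label: .9375 (large) or .875 (medium).

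**2. Slower learning, half credit, k further zero probes after teaching starts.** With probe 1: (n − 0.5(1 + k))/n. Without it: (n − 1 − 0.5k)/(n − 1).
- k = 1: at n = 8, 7/8 = .875 becomes 6.5/7 = .929; at n = 13, 12/13 = .923 becomes 11.5/12 = .958; at n = 14, 13/14 = .929 is already large. The label changes at 8–13 probes.
- k = 2, the series 0, 0, 0, 25, 50, 75, 75, 75: 6.5/8 = .8125 becomes 6/7 = .857, medium both times.

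**3. Active versus active (RQs 5 and 11), half credit.** If every later probe of the upper set exceeds every later probe of the lower, and the lower is above 0%, NAP is [n(n − 1) + 0.5]/n²: 56.5/64 = .883 at 8; 90.5/100 = .905 at 10; 132.5/144 = .920 at 12. It is 1.00 without probe 1. This is a demanding case. Upper 0, 50, then 75 × 8 against lower 0, 25, then 50 × 8 gives .865 with the probe and .951 without. With the conditions swapped at n = 8, NAP is 1 − .883 = .117, in the weak band, although the sets are fully separated.

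**4. Simulation under an assumed curve.** Score at probe t is Binomial(4, 1 − exp(−r(t − 1))). The mastery and cap rules are applied, a mastered set is held at its mastery-session probability, and control is 0. There are 4,000 runs for each rate pair: (.1,.1), (.2,.2), (.3,.3), (.5,.5), (.2,.1), (.3,.15), (.5,.25), (.4,.1). Counting both active sets, with half credit and rounded bands:
- Dropping probe 1 raises mean effectiveness NAP from about .87–.95 to .91–.99.
- The label changes in about 15–46% of runs.
- The 4-probe ending occurs in at most about 0.4% of runs.
- For two sets with identical learning, values at or above .66 or at or below .34 rise from about 0.6–4.4% to 1.4–14.4%.

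**The case against.** The strongest reply is that no conclusion depends on this. Visual analysis is primary, NAP informs one of five features, and no decision uses a band. That stands, and it caps the severity.

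A second reply is that keeping the probe is defensible: it is common to all conditions, pulls toward no difference, and keeps NAP on the same data as the graph. The last part stands, so the probe should be reassigned on the graphs too and not in NAP alone. Zeros after teaching also lower NAP, so the untaught probe is not the only cause of a medium label.

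A reader might infer more than the documents support in four places.
- *That the plan contradicts itself on ties, because it calls Tau a linear re-scaling of NAP.* That needs Tau to be wins minus losses over all pairs, a definition the plan does not give. What stands is that no tie rule is written and that the literal wording credits none.
- *That direction is undefined.* It is written for the eight effectiveness questions. For the efficiency questions the plan credits the higher path, and with half credit the two orientations sum to 1. Only the A/B assignment is missing. Tables 2 and 3 do not supply it: Condition 1 is the hypothesised better condition for feedback in RQs 5 and 6, but the hypothesised worse one for spacing in RQs 11 and 12.
- *That label changes are more frequent than shown.* Without rounding, .929 at 7 probes would count as medium and the simulated share would rise. The bands are printed to two decimals with a gap between .92 and .93, so rounding is the natural reading.
- *That retention is affected.* The untaught probe does not enter the maintenance contrasts.

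**Conclusion.** The point holds and is minor. That the probe is untaught, and that nothing excludes it, follows directly from the text. In the clean case it costs 0.5/n of active-versus-control NAP with half-credit ties: .125 at 4 probes, .083 at 6 and .0625 at 8. That changes the rounded label at 4–6 probes. With slower learning the label may change in longer series or not at all. For RQs 5 and 11 the pull is toward .50, so the probe lowers NAP only when the better condition is the one credited.

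These figures rest on 0% for the untaught probe and the control. The simulated 15–46% depends on a learning curve that the documents do not supply; it is an illustration and not a forecast. It would be wrong to infer that any finding on a functional relation would be overturned, because no conclusion is tied to a NAP value or label.

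**What to change.** Add to Section 8.0, before analysis:
- For the acquisition contrasts (RQs 1, 2, 5, 7, 8 and 11), treat the first comparison-phase probe as the last baseline point in every condition, and mark it so on the graphs, so that NAP and visual analysis cover the same data.
- NAP compares two conditions within a phase: (non-overlapping pairs + 0.5 × ties) / all pairs.
- For RQs 5, 6, 11 and 12, orient NAP by the Section 2.0 hypotheses (feedback over no feedback, spaced over massed), and report values below .50 as favouring the other condition and not as weak.

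The mastery and phase-ending rules are not touched, and no new data are needed. The cost is one fewer point per condition and so a more variable NAP. Under the assumed curve, the share of apparent differences between two identically learned sets rises from about 0.6–4.4% to 1.4–14.4%, with the upper figures at the fastest learning rate. The efficiency results should be read with that in mind, given eight participants per factor.
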